Appendix 2. IWG Criteria: Response Criteria and Progression Definitions for Myelodysplasia***

Response Criteria (responses CR, PR, mCR must last at least 4 weeks)	Peripheral Blood				Bone Marrow Blasts (BMB) (%)	Other
	Hgb(g/dL)	Neutrophils (L)	Platelets (L)	Blasts (%)		
Complete Remission (CR)**	≥11	≥1 x 10 ⁹	≥100 x 10 ⁹	0	≤5	Normal maturation of all cell lines, note if has persistent dysplasia
Partial Remission (PR)**					Decreased by ≥50% but still >5%	All CR criteria if abnormal before treatment except BMB
Marrow CR (mCR)	If hematologic improvement (HI) response, note in addition to Marrow CR				≤5% & decreased by ≥50%	
Stable Disease*						Failure to achieve PR & no evidence of progression*
Failure						Death, or disease progression: worsening cytopenia, increase in % BM blasts, progression to a more advanced MDS FAB subtype
Relapse after (m)CR or PR					ICH	At least one of the following: Return to pre-treatment BMB % Decrement of ≥50% from maximum remission/response levels in granulocytes or platelets Reduction in Hgb ≥1.5g/dL or transfusion dependence

*SD must last >8 weeks but response is documented regardless of duration.

**Stability of the improved counts is sufficient to define CR or PR without the need to repeat a second BM.

***This criteria will be applied to MDS patients enrolled in the Safety Lead-In and Expansion components of the study and patients with AML with 20-30% blasts and multi-lineage dysplasia and CMML without proliferative disorder enrolled into the Safety Lead-In component of the study.

Additional Response Criteria for Myelodysplasia***

Cytogenetic Response Complete Partial	Disappearance of chromosomal abnormality with no appearance of new ones $\geq 50\%$ reduction of chromosomal abnormality
Disease Progression For patients with % blasts at screening: <5% bone marrow blasts 5-10% bone marrow blasts 11-20% bone marrow blasts 21-30% bone marrow blasts For all categories, any of:	$\geq 50\%$ increase to >5% bone marrow blasts $\geq 50\%$ increase to >10% bone marrow blasts $\geq 50\%$ increase to >20% bone marrow blasts $\geq 50\%$ increase to >30% bone marrow blasts At least 50% decrease from maximum remission/response in granulocytes or platelets Reduction in Hgb by ≥ 2 g/dL Transfusion dependence

Proposed modified IWG Myelodysplasia Response Criteria for Hematologic Improvement (HI)**

[figure not shown]
Erythroid response (pre-treatment <11g/dL)*	Hgb increase by ≥ 1.5 g/dL Relevant reduction of units of RBC transfusions by an absolute number of at least 4 RBC transfusions/8 weeks as compared to the pretreatment transfusion number in the previous 8 weeks (only RBC transfusions given for Hb ≤ 9 g/dL pretreatment will count in the RBC transfusion evaluation).
Platelet Response (pretreatment <100 x10 ⁹ /L)*	Absolute increase of ≥ 30 x10 ⁹ /L if starting with >20 x 10 ⁹ /L platelets Increase from <20 x 10 ⁹ /L to >20 x10 ⁹ /L and by at least 100%
Neutrophil Response (pretreatment <1 x 10 ⁹ /L)*	At least a 100% increase and an absolute increase >0.5 x10 ⁹ /L
Progression or relapse after HI in the absence of another explanation	At least one of the following: 
 • At least 50% decrease from maximum response levels in granulocytes or platelets; • Reduction in Hgb by ≥ 1.5g/dL; • Transfusion dependence.

*Pretreatment counts averages of at least 2 measurements (not influenced by transfusions) ≥ 1 week apart.

** Hematologic Improvement must last ≥ 8 weeks and is derived based on lab data entered in the database.

***This criteria will be applied to MDS patients enrolled in the Safety Lead-In and Expansion components of the study and patients with oligoblastic AML and CMML without proliferative disorder enrolled into the Safety Lead-In component of the study.

Appendix 3. Myelodysplastic Syndromes: 2014 Update on Diagnosis, Risk-Stratification, and Management*

* Applies to MDS patients enrolled in the Safety Lead-In and Expansion components of the study and patients with AML with 20-30% blasts and multi-lineage dysplasia and CMML without proliferative disorder enrolled into the Safety Lead-In component of the study.

Source: Schanz J, Tüchler H, et al. New comprehensive cytogenetic scoring system for primary myelodysplastic syndromes (MDS) and oligoblastic acute myeloid leukemia after MDS derived from an international database merge. J Clin Onc 2012; 30:820-29.

Figure from Garcia-Manero G. Myelodysplastic syndromes: 2014 update on diagnosis, risk stratification, and management. American Journal of Hematology 2014; 89(1):97-108.

Appendix 4. Strong CYP3A4/5 Inducers

Strong CYP3A4/5 Inducers	
Inducer	Therapeutic Class
Rifampin	Antibiotics
Rifabutin	Antibiotics
Avasimibe	Antilipidemics
Phenytoin	Anticonvulsants
Carbamazepine	Anticonvulsants
Phenobarbital	Anticonvulsants
Enzalutamide	Antiandrogens
St. John's Wort	Herbal Medications
Mitotane	Antineoplastic
Moderate CYP3A4/5 Inducers	
Inducer	Therapeutic Class
Semagacestat	Alzheimers
Efavirenz	Non-nucleoside Reverse Transcriptase Inhibitors (NNRTI)
Bosentan	Endothelin Receptor Antagonist
Genistein	Food Product
Thioridazine	Antipsychotics
Nafcillin	Antibiotics
Talviraline	NNRTI
Lopinavir	Protease Inhibitor
Modafinil	Psychostimulant
Etravirine	NNRTI
Lersivirine	NNRTI

Source: University of Washington Drug Interaction Database. "Copyright University of Washington 1999-2015, UW Metabolism and Transport Drug Interaction Database, accessed: May 2017".

Appendix 5. List of Drugs with Known Risk of Torsade de Pointes

The following drugs are known to have the risk of Torsade de Pointes due to QTc prolongation and their current use in combination with glasdegib is not recommended. If any of these drugs are considered to be medically necessary, then they should be used with caution in combination with glasdegib.

Generic Name	Drug Class	Therapeutic Use	Route
Amiodarone	Anti-arrhythmic	Abnormal heart rhythm	oral, injection
Anagrelide	Phosphodiesterase 3 inhibitor	Thrombocytopenia	oral
Arsenic trioxide	Anti-cancer	Leukemia	injection
Astemizole (Off US mkt)	Antihistamine	Allergic rhinitis	oral
Azithromycin	Antibiotic	Bacterial infection	oral, injection
Bepidil (Off US mkt)	Anti-anginal	Heart pain	oral
Chloroquine	Anti-malarial	Malaria infection	oral
Chlorpromazine	Anti-psychotic / Anti-emetic	Schizophrenia/ nausea	oral, injection, suppository
Cilostazol	Phosphodiesterase 3 inhibitor	Intermittent claudication	oral
Ciprofloxacin	Antibiotic	Bacterial Infection	oral, injection
Cisapride (Off US mkt)	GI stimulant	Heartburn	oral
Citalopram	Anti-depressant, SSRI	Depression	oral
Clarithromycin	Antibiotic	Bacterial infection	oral
Disopyramide	Anti-arrhythmic	Abnormal heart rhythm	oral
Dofetilide	Anti-arrhythmic	Abnormal heart rhythm	oral
Domperidone (Not on US mkt)	Anti-nausea	Nausea	oral, injection, suppository
Donepezil	Cholinesterase inhibitor	Dementia	oral
Dronedarone	Anti-arrhythmic	Atrial Fibrillation	oral
Droperidol	Anti-psychotic / Anti-emetic	Anesthesia adjunct, nausea	injection
Erythromycin	Antibiotic	Bacterial infection; increase GI motility	oral, injection
Escitalopram	Anti-depressant, SSRI	Major depression/ Anxiety disorders	oral
Flecainide	Anti-arrhythmic	Abnormal heart rhythm	oral
Fluconazole	Anti-fungal	Fungal infection	oral, injection
Gatifloxacin (Off US mkt)	Antibiotic	Bacterial infection	oral, injection

Generic Name	Drug Class	Therapeutic Use	Route
Grepafloxacin (Off market worldwide)	Antibiotic	Bacterial infection	oral
Halofantrine	Anti-malarial	Malaria infection	oral
Haloperidol	Anti-psychotic	Schizophrenia, agitation	oral, injection
Ibutilide	Anti-arrhythmic	Abnormal heart rhythm	injection
Levofloxacin	Antibiotic	Bacterial infection	oral, injection
Levomethadyl (Off US mkt)	Opiate	Pain control, narcotic dependence	oral
Mesoridazine (Off US mkt)	Anti-psychotic	Schizophrenia	oral
Methadone	Opiate	Pain control, narcotic dependence	oral, injection
Moxifloxacin	Antibiotic	Bacterial infection	oral, injection
Ondansetron	Anti-emetic	Nausea, vomiting	oral, injection
Pentamidine	Antibiotic	Pneumocystis pneumonia	injection, inhaled
Pimozide	Anti-psychotic	Tourette's tics	oral
Probucol (Off US mkt)	Antilipemic	Hypercholesterolemia	oral
Procainamide (Oral off US mkt)	Anti-arrhythmic	Abnormal heart rhythm	injection
Propofol	Anesthetic	Anesthesia	injection
Quinidine	Anti-arrhythmic	Abnormal heart rhythm	oral, injection
Sevoflurane	Anesthetic, general	Anesthesia	inhaled
Sotalol	Anti-arrhythmic	Abnormal heart rhythm	oral
Sparfloxacin (Off US mkt)	Antibiotic	Bacterial infection	oral
Sulpiride (Not on US mkt.)	Anti-psychotic, atypical	Schizophrenia	oral
Terfenadine (Off US mkt)	Antihistamine	Allergic rhinitis	oral
Thioridazine	Anti-psychotic	Schizophrenia	oral
Vandetanib	Anti-cancer	Thyroid cancer	oral

US mkt = United States Market.

Source: Credible Meds.org (<http://crediblemeds.org/healthcare-providers/drug-list/?rf=All>).
 TdP risk category filtered on Drugs with known TdP risk. Assessed 11 October 2015.

Appendix 6. Strong CYP3A4/5 Inhibitors

Strong CYP3A4/5 Inhibitors	
Inhibitor	Therapeutic Class
Ketoconazole	Antifungal
Itraconazole	Antifungal
Voriconazole	Antifungal
Posaconazole	Antifungal
Troleandomycin	Antibiotics
Clarithromycin	Antibiotics
Telithromycin	Antibiotics
Mibefradil	Calcium Channel Blocker
Conivaptan	Diuretics
Nefazodone	Antidepressants
Cobicistat	--
Indinavir/Ritonavir	Protease Inhibitors
Tipranavir/Ritonavir	Protease Inhibitors
Ritonavir	Protease Inhibitors
Indinavir	Protease Inhibitors
Nelfinavir	Protease Inhibitors
Saquinavir	Protease Inhibitors
Saquinavir/Ritonavir	Protease Inhibitors
Lopinavir/Ritonavir	Protease Inhibitors
Telaprevir	Antivirals
Boceprevir	Antivirals
Danoprevir/Ritonavir	Antivirals
Elvitegravir/Ritonavir	Antivirals
LCL161	Cancer treatment
Idelalisib	Kinase Inhibitors
Grapefruit Juice DS	Food Products

Source: University of Washington Drug Interaction Database. "Copyright University of Washington 1999-2015. UW Metabolism and Transport Drug Interaction Database, accessed: 11 October 2015."

Appendix 7. Moderate CYP3A4/5 Inhibitors

Moderate CYP3A4/5 Inhibitors	
Inhibitor	Therapeutic Class
Fluconazole	Antifungals
Erythromycin	Antibiotics
Ciprofloxacin	Antibiotics
Diltiazem	Calcium Channel Blockers
Verapamil	Calcium Channel Blockers
Dronedarone	Antiarrhythmics
Aprepitant	Antiemetics
Casopitant	Antiemetics
Netupitant	Antiemetics
Tofisopam	Benzodiazepines
Cyclosporine	Immunosuppressant
Schisandra sphenanthera	Herbal Medication
ACT-178882	Renin Inhibitor
Cimetidine	H2 Receptor Antagonist
FK1706	Central Nervous System Agent
Faldaprevir	Antivirals
Crizotinib	Kinase Inhibitor
Nilotinib	Kinase Inhibitor
Atazanavir/Ritonavir	Protease Inhibitor
Darunavir	Protease Inhibitor
Darunavir/Ritonavir	Protease Inhibitor
Atazanavir	Protease Inhibitor
Amprenavir	Protease Inhibitor
Imatinib	Antineoplastic agent
Grapefruit Juice	Food Products

Source: University of Washington Drug Interaction Database. "Copyright University of Washington 1999-2015. UW Metabolism and Transport Drug Interaction Database, accessed: 11 October 2015."

Appendix 8. Laboratory Assessments

Hematology	Blood Chemistry	Urinalysis (microscopic analysis)	Coagulation Tests
Hemoglobin	ALT	If urine dipstick is positive for protein, perform urinalysis (U/A) with microscopic. If U/A with microscopic shows $\geq 2+$ protein, collect 24-hour urine for protein.	aPTT
Platelets	AST	Urine dipstick for urine blood: If positive, collect a U/A with microscopic (unless hematuria can be explained by local bleeding such as menses).	INR
WBC	Alk Phos	Specific Gravity	
Neutrophils	Sodium	PH	
Lymphocytes	Potassium	Protein	
Monocytes	Magnesium	Glucose	
Eosinophils	Chloride	RBC	
Basophils	Calcium	WBC	
Bands	Total Bilirubin	Ketones	
Blast Count	BUN or Urea	Leukocyte Esterase	
	Creatinine	Casts	
	Uric Acid	Crystals	
	Glucose (non-fasting)	Nitrate	
	Albumin		
	Total Protein		
	Phosphorus		
	LDH		
	CPK		
	Bicarbonate		
	B12*		

* Applies to Safety Lead-In patients only: Needed only at Screening Visit only for eligibility requirement.

Appendix 10. IPSS-R Classification System for Myelodysplastic Syndromes*

Prognostic variable	0	0.5	1	1.5	2	3	4
Cytogenetics	Very Good		Good		Intermediate	Poor	Very Poor
Bone Marrow Blast %	≤2		>2 to <5		5-10	>10	
Hemoglobin	≥10		8 to <10	<8			
Platelets	≥100	50-<100	<50				
ANC	≥0.8	<0.8					
Risk Category				Risk Score			
Very Low				≤1.5			
Low				>1.5-3			
Intermediate				>3-4.5			
High				>4.5-6			
Very High				>6			

Adapted from Greenberg PL et al. Revised International Prognostic Scoring System for Myelodysplastic Syndromes. Blood 2012; 120(12) 2454-2465.

*Only applies to MDS patients enrolled in the Expansion component of the study.

Appendix 11. 2017 ELN Response Criteria for Acute Myeloid Leukemia

Response Criteria	Neutrophils (μL)	Platelets (μL)	Bone Marrow Blasts (%)	Other
Complete Remission without Minimal Residual Disease (CR_{M RD})				If studied pretreatment, CR with negativity for a genetic marker by RT qPCR, or CR with negativity by multiparameter flow cytometry
Morphologic Complete Response (CR)	$\geq 1,000$	$\geq 100,000$	<5; no peripheral blasts; no blasts with Auer rods	No EMD; Transfusion independent
Complete Remission with partial hematologic recovery (CRh)¹	>500	>50,000	<5; no peripheral blasts; no blasts with Auer rods	No EMD; Not qualifying for CR
Morphologic CR with incomplete blood count recovery (CRi)	<1,000 -or-	<100,000	<5; no peripheral blasts; no blasts with Auer rods	No EMD; Either neutrophils or platelets not recovered; Not qualifying for CRh
Morphologic leukemia-free state (MLFS)	<1,000 -and-	<100,000	<5; no blasts with Auer rods	No EMD; Neutrophils and platelets not recovered; BM not merely “aplastic”; BM cellularity must be 10%, or 200 cells enumerated; Not qualifying for CRi
Partial remission (PR)	$\geq 1,000$	$\geq 100,000$	blasts decrease to 5-25 and $\geq 50\%$ decrease from pretreatment	Blasts $\leq 5\%$ if Auer rod positive
Stable Disease (SD)				Absence of CR _{M RD} , CR, CRh, CRi, PR, MLFS and criteria for PD not met. Should last at least 3 months.

Progressive Disease (PD)			>50% increase in blasts from pretreatment (if baseline is <30% blasts, must have at least 15% increase; or >70% blasts for ≥3 months; no improvement in ANC (>0.5 x 10 ⁹ /L [500 μL], and/or platelet count to >50 x 10 ⁹ /L [50 000 μL nontransfused]); or > 50% increase in peripheral blasts (WBC count x % blasts) to >25 x 10 ⁹ /L (25000 μL); or new EMD
Relapse			
Hematologic relapse (after CRMRD-, CR, CRi)			Bone marrow blasts >5%; or Reappearance of blasts in the blood; or Development of EMD
Molecular Relapse (after CRMRD-)			If studied pretreatment, reoccurrence of MRD as assessed by RT-qPCR or multiparameter flow cytometry
Treatment Failure			
Primary refractory disease	For Non Intensive: Treatment Failure is defined as failure to achieve CR or CRh following up to 6 cycles of study treatment.		
Death in aplasia	Deaths occurring ≥7 days following completion of initial treatment while cytopenic; with an aplastic or hypoplastic bone marrow obtained within 7 days of death, without evidence of persistent leukemia.		
Death from indeterminate cause	Deaths occurring before completion of therapy, or <7 days following its completion or deaths occurring ≥7 days following completion of initial therapy with no blasts in the blood, but no bone marrow examination available.		

ANC=Absolute neutrophil count; WBC=white blood cell; EMD=extramedullary disease.

There is no minimum requirement for bone marrow cellularity or hemoglobin concentration for response criteria.

Composite from Cheson, BD, Bennett JM, Kopecky KJ, et al. Revised recommendations of the International Working group for diagnosis, standardization of response criteria, treatment on outcomes and reporting standards for therapeutic trials in acute myeloid leukemia. J Clin Oncol 2003; 21(24)4642-4649⁴⁰ and Döhner H, Estey E, Grimwade D, et al. Diagnosis and management of AML in adults: 2017 ELN recommendations from an international expert panel. Blood 2017;129(4): 424-47.⁴²

¹CRh is not part of the 2017 ELN recommendations, but is a required assessment for this study.

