combination with chemotherapy was consistent with what was seen in an earlier monotherapy study in patients with selected myeloid malignancies. A similar population of newly diagnosed elderly AML patients was enrolled into a Phase 3 study of decitabine vs supportive care vs low dose cytarabine where the CR+ CRi rate was 25.6% in the decitabine only arm.

In the Phase 2 portion of Study B1371003, a prospective, randomized (2:1), open-label clinical trial in 132 previously untreated AML patients who were not candidates for intensive chemotherapy based on age or other risk factors and higher risk MDS, the addition of glasdegib 100 mg orally PO Qday to LDAC vs LDAC alone resulted in a significant improvement in OS (mOS 8.8 months (80% CI: 6.9, 9.9) vs 4.9 months (80% CI: 3.5, 6.0); hazard ratio [HR] 0.513 [80 % CI: 0.394-0.666]; 1-sided p-value=0.0004). The CR/CRi rate for AML patients in the glasdegib + LDAC arm was 25% (80% CI: 19.1, 30.9) vs 4.5% (80% CI: 0.5, 8.6) in the LDAC alone arm. The safety/tolerability profile was consistent with that in elderly AML patients receiving chemotherapy.

Glasdegib, which targets the Hh pathway component Smoothed (SMO), is an oral inhibitor of the Hh pathway currently in clinical development for patients with myeloid malignancies. The Hedgehog (Hh) signaling pathway regulates cell differentiation and self-renewal in the developing embryo, and is typically silenced in adult tissues. Aberrant Hh signaling in the post-embryonic stage may result from mutations in key pathway genes, non-mutational mechanisms related to the secretion of Hh ligands, or signals from cells in the tumor microenvironment. Aberrant Hh signaling has been identified in a variety of human myeloid malignancies, and specifically in leukemia stem cells (LSCs).

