8.2.2.2.2. Other Efficacy Measures

Specifically, for AML cohort, the following binary efficacy endpoints (with 95% exact CI) will be summarized in frequency tables, proportion of patients achieving CR, CRh, CRi, CR/CRi, MLFS, PR, SD, CRc, , CRm, and CR+PR.

For MDS cohort, the following binary efficacy endpoints (with 95% exact CI) will be summarized in frequency tables, proportion of patients achieving CR, marrow CR, PR, SD, CR+PR, and Partial or Complete Cytogenetic Response, as well as the proportion of patients ever achieving HI.

The FAS will be used.

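### The AML composite CR/CRi in SAP 8.2.2.2.2 leaves out CRh under the protocol's response table, and its value depends on whether Protocol Appendix 11 or SAP Appendix 4 is programmed

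*Protocol*

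**What the plan says.** Protocol 7.7.1 applies the criteria in Appendix 11 to all AML patients in the expansion and adds CRh as an assessment. In Appendix 11 the classes are nested. CRh needs ANC above 500/µL, platelets above 50,000/µL and fewer than 5% marrow blasts, and carries the note "No EMD; Not qualifying for CR". CRi needs ANC below 1,000 or platelets below 100,000, and carries the note "Either neutrophils or platelets not recovered; Not qualifying for CRh". CR needs ANC of at least 1,000, platelets of at least 100,000 and transfusion independence. For non-intensive therapy the same appendix states: "Treatment Failure is defined as failure to achieve CR or CRh following up to 6 cycles of study treatment". Its relapse row begins "Hematologic relapse (after CRMRD-, CR, CRi" and does not name CRh.

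SAP 8.2.2.2.2 lists the AML binary endpoints as "proportion of patients achieving CR, CRh, CRi, CR/CRi, MLFS, PR, SD, CRc, , CRm, and CR+PR", each with an exact 95% CI. The visible composites are CR/CRi and CR+PR.

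SAP Appendix 4 has its own version of the response table. It contains the CRh row, but its CRi row does not exclude patients who qualify for CRh, and its SD row does not list CRh among the responses that must be absent. It has no relapse row.

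**The concern.** A composite remission rate should be a union of adjacent classes: once a lower class counts, every class above it should count too. Under the protocol table, CR/CRi breaks that rule. It includes patients whose best response is CRi, whom the protocol calls treatment failures, and excludes CRh patients, whom it does not.

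Both documents contain a response table, and the tables disagree on CRi. Protocol Section 9 allows the SAP to modify the protocol's plans, so it is not obvious which table a programmer should follow for this rate. What is at stake is the meaning and reproducibility of one published secondary rate.

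**Working it through.** **1. Interval method.** Protocol 9.1.2 gives a maximum width of 0.374 for the exact two-sided 95% CI with 30 patients. For x responders out of n, the limits are the 0.025 quantile of Beta(x, n−x+1) and the 0.975 quantile of Beta(x+1, n−x). Over x = 0 to 30 with n = 30, the largest width is 0.3741, at x = 15. The plan's figure is reproduced.

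**2. Classification.** Take patients with fewer than 5% marrow blasts, no peripheral blasts, no Auer rods and no extramedullary disease, and apply each table row by row (counts per µL):

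| ANC | Platelets | Transfusion independent | Protocol Appendix 11 | In CR/CRi? | SAP Appendix 4 | In CR/CRi? |
|---|---|---|---|---|---|---|
| 1,500 | 150,000 | yes | CR | yes | CR | yes |
| 1,500 | 150,000 | no | CRh | no | CRh | no |
| 700 | 150,000 | either | CRh | no | CRh and CRi | yes |
| 1,500 | 70,000 | either | CRh | no | CRh and CRi | yes |
| 700 | 70,000 | either | CRh | no | CRh; also CRi if the CRi row's or is inclusive | depends |
| 300 | 150,000 | either | CRi | yes | CRi | yes |
| 1,500 | 30,000 | either | CRi | yes | CRi | yes |

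Under the protocol table, all four CRh patterns are left out and both CRi patterns are counted. Under the SAP table, the two CRh patterns with one unrecovered lineage are counted, the pattern with both lineages partly recovered depends on how or is read, and the pattern with full counts but continuing transfusion is left out. That last pattern is outside CR/CRi under both tables.

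**3. Size.** With n = 30, each omitted patient changes the rate by 1/30 = 3.3 percentage points. The documents give no CRh or CRi frequency, so the counts below are assumptions: 8 CR, 2 CRi, h patients with CRh, and each patient in one class. Under the protocol table CR/CRi = (8+2)/30 = 33.3% (95% CI 17.3 to 52.8) for every h. The union is (10+h)/30:

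| h | CR+CRh+CRi | 95% CI | Difference from CR/CRi (points) |
|---|---|---|---|
| 1 | 11/30 = 36.7% | 19.9 to 56.1 | 3.3 |
| 2 | 12/30 = 40.0% | 22.7 to 59.4 | 6.7 |
| 3 | 13/30 = 43.3% | 25.5 to 62.6 | 10.0 |
| 4 | 14/30 = 46.7% | 28.3 to 65.7 | 13.3 |
| 6 | 16/30 = 53.3% | 34.3 to 71.7 | 20.0 |

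Under the SAP table, CR/CRi lies somewhere between 10/30 and (10+h)/30, depending on how many CRh patients have only one unrecovered lineage. With h = 3 that is anywhere from 33.3% to 43.3%.

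**The case against.** The strongest objection is that CR/CRi is a SAP endpoint and should be read with the SAP's own table, where many CRh patients already count as CRi. This stands in part: it is wrong to say without qualification that the composite omits CRh. But Protocol 7.7.1 points to Appendix 11 for AML response. Even under SAP Appendix 4 the full-count, transfusion-dependent patient is left out, and the patient with both counts partly recovered depends on the reading of or.

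A second objection is that CRh has its own line, so a reader can add it. That works only if the classes are mutually exclusive. Protocol 9.3.6 reports the proportion ever reaching each endpoint, and neither document says the AML rates are by best response. Such rates can overlap, so neither their sum nor an exact CI for the union can be recovered from the separate lines.

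A third objection is redaction. The SAP list has a gap and other response text is blacked out, so a CRh composite may exist elsewhere. That is possible, but the visible CR/CRi composite has this defect regardless.

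A reader might also draw stronger conclusions, which the documents do not support:

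- *The rate falls when patients improve from CRi to CRh.* With the ever-achieving rule in Protocol 9.3.6, a patient who was once CRi stays in CR/CRi.
- *The rate is biased low against the quoted external figures* (25% with glasdegib plus LDAC, 25.6% with decitabine). The CRi definitions behind those figures are not given, and no comparison with them is planned. The futility rule uses CR alone.
- *CR+PR should become a rate of PR or better that includes CRh, CRi and MLFS.* PR requires full count recovery, which CRh and CRi generally lack, so ranking them above PR rests on blast clearance and table order. That is a preference rather than a correction.
- *The relapse row distorts an analysis.* The visible duration endpoints start from CR, or from CR or PR. None measures relapse after CRh.

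**Conclusion.** The point holds as a defect in one secondary AML rate. Under Protocol Appendix 11, CR/CRi skips a class that the protocol ranks above CRi. Across the two documents, the rate is not uniquely defined. At n = 30 the cost is 3.3 points for each patient who reaches CRh without ever being counted as CR or CRi; how many such patients there will be is unknown. The primary CR rate, its confidence interval and the futility boundaries are untouched, and SAP 4.1 states that there are no formal hypotheses.

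One assumption matters for the full-count, transfusion-dependent patient. The CRh row states no transfusion requirement, so I read that patient as CRh. Protocol 7.7.1 describes CRh as CR with lower count limits and could be read as keeping the requirement. In that case the patient is outside CRh as well as outside CR/CRi.

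**What to change.** - In SAP 8.2.2.2.2, replace CR/CRi for AML with CR+CRh+CRi, defined as the proportion of patients who achieve any of the three, with an exact 95% CI. Keep the single-category rates. The new total does not depend on where the line between CRh and CRi is drawn.
- In SAP Appendix 4, align the CRi and SD rows with Protocol Appendix 11, so that CRi excludes patients who qualify for CRh and SD requires the absence of CRh.
- As a consistency edit, add CRh to the hematologic relapse row of Protocol Appendix 11. SAP Appendix 4 has no such row and needs no matching change. Protocol 5.4.4 refers to relapse when it describes treatment duration, so the sponsor should check that the passages still agree; I take no position on treatment.

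The cost is SAP wording and a replaced line in a frequency table, with no new data. Because the change does not touch the primary endpoint, Protocol Section 9 does not require an amendment for the SAP edits; the relapse row can go into the next one. The new rate cannot be lower than CR/CRi, so it must be labelled clearly and not presented as the same quantity.
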